4.2 Exclusion

1. Active inflammatory gastrointestinal disease such as chronic diarrhea (unless related to underlying malignancy or prior related treatment) or history of abdominal fistula, gastrointestinal perforation, peptic ulcer disease, or intra-abdominal abscess within 6 months prior to study enrollment. Gastroesophageal reflux disease under treatment with proton pump inhibitors is allowed.
2. Pregnancy or breast feeding
3. Current active treatment in another clinical study
4. Active bacterial, fungal or viral infection including hepatitis B (HBV), hepatitis C (HCV)
5. Known human immunodeficiency virus (HIV) or acquired immunodeficiency syndrome (AIDS)-related illness that is not well controlled.
6. Active or prior plasma cell leukemia (defined as either 20% of peripheral WBC comprised of plasma/CD138+ cells or an absolute count of $2 \times 10^9/L$)
7. Solitary bone or solitary extramedullary plasmacytoma as the only evidence of plasma cell dyscrasia.
8. Subjects with serum calcium (corrected for albumin) $\geq 12 \text{ mg/dL}$
9. Any of the following in the previous 6 months: myocardial infarction, severe/unstable angina, coronary/peripheral artery bypass graft, symptomatic congestive heart failure, cerebrovascular accident, transient ischemic attack or symptomatic pulmonary embolism.
10. Other severe acute or chronic medical or psychiatric condition or laboratory abnormality that may increase the risk associated with study participation or study drug administration, or may interfere with the interpretation of study results, or in the judgment of the investigator would make the patient inappropriate for entry into the study.
11. Actively receiving medications that have risk of Torsades de Pointes or are strong cytochrome P450 inhibitors or inducers.

4.3 Contraception

During the study, fertile female patients must take precautions to prevent pregnancy since the effects of the study medication on the fetus are unknown. Male patients with partners of childbearing potential must take precautions to prevent pregnancy of the partner since the effects of this drug on sperm are unknown. These restrictions should remain in force for 90 days from the last dose of investigational agent. Drug interaction studies with oral contraceptives have not been performed, so barrier methods of contraception or abstinence should be considered. The definition of effective contraception should be in agreement with local regulation and based on the judgment of the principal investigator or a designated associate. A suggested definition of adequate contraception is the use of double barrier contraception (e.g., condom plus spermicide in combination with a female condom, diaphragm, cervical cap or intrauterine device).

5 STUDY TREATMENTS

5.1 Drug Supply

5.1.1 Formulation, Packaging and Storage

The study drug ONC201 is provided as a dihydrochloride salt (125 mg free base; ~150mg disalt), along with microcrystalline cellulose, filled into hydroxypropyl methylcellulose (HPMC) capsule shells.

The ONC201 drug product capsules are intended for oral administration. The product is stored in a multi-dose container. The capsules are packaged in high-density polyethylene (HDPE) white opaque bottles, closed with an induction seal and capped with a white ribbed SecuRx® polypropylene (PPE) cap. The capsules are to be stored in the original closed container at room temperature (15 to 30°C).

The study drug bottle label bears the following information:

[figure not shown]

Figure 3.1: Investigational drug label

5.1.2 Drug Accountability

Upon receipt at the investigative site, study drug product must be stored at room temperature in the original packaging. The drug should be protected from light and excessive humidity in a monitored, locked, secure area with limited access. Storage area temperature conditions must be monitored and recorded daily. All temperature excursions will be reported to the sponsor for assessment and authorization for continued use. Study site staff must instruct patients on how to store and administer oral study drug agents that are dispensed for at-home administration.

Accountability for study drug product is the responsibility of the investigator. The study site must maintain accurate records demonstrating dates and amount of study treatment received, to whom dispensed (patient-by-patient accounting), and accounts of any study treatment accidentally or deliberately destroyed. A written explanation must be provided for any discrepancies. Patients are to be instructed on proper accountability of the take-home study

drugs and will be instructed to return any unused drug in the original packaging along with their completed diary cards at the appropriate clinic visits. The investigator must destroy or return all unused drug product provided.

5.2 ONC201 Administration

Patients will receive 625 mg of ONC201 on an outpatient basis. The study drug, ONC201, will be supplied in capsule form for oral dosing. Patients should take designated capsules of ONC201 at approximately the same time on each day of drug administration. Patients will be instructed to not eat for 2 hours pre and 2 hours post dosing. If the patient vomits after taking ONC201, they should not retake the dose. Missed doses will not be made up.

ONC201 should be taken with a glass of water and consumed over as short a time as possible. Patients should swallow the capsules as a whole and not chew them. Do not crush or empty the capsule. If vomiting occurs during the course of treatment, no re-dosing of the patient is allowed before the next scheduled dose. The occurrence and frequency of any vomiting during a treatment cycle must be noted as an adverse event. In addition, on the days of drug administration the exact time of any episodes of vomiting within the first 4 hours post-dosing on that day must be noted whenever possible.

Dexamethasone will be obtained and administered per standard of care guidelines for multiple myeloma patients. Administration of dexamethasone is recommended approximately 6 hours (+ 2 hours) after ONC201.

5.3 General Concomitant Medication and Supportive Care Guidelines

Because there is a potential for interaction of ONC201 with other concomitantly administered drugs through the cytochrome P450 system, the case report form will capture the concurrent use of all other drugs, over-the-counter medications, and/or alternative therapies. Concomitant medications that have risk of Torsades de Pointes, or are strong cytochrome P450 inhibitors or inducers, are not allowed.

Any medication taken by a subject during the course of the study and the reason for its use will be documented in the source documents and case report form (CRF) that will be provided by the Sponsor.

5.4 Duration of Therapy

In the absence of treatment delays due to adverse event(s), treatment may continue once every weeks until one of the following criteria applies:

- Disease progression
- Intercurrent illness that prevents further administration of treatment
- Unacceptable adverse event(s)
- Patient decides to withdraw from the study
- General or specific changes in the patient's condition that render the patient unacceptable for further treatment in the judgment of the investigator.

- The Sponsor chooses to discontinue the study: for example if severe or life threatening toxicities are encountered by other enrolled patients in the clinical trial or the dose to pharmacokinetics or pharmacodynamics relationship plateaus.

Patients will be followed for three years after removal from study or until death, whichever occurs first. Patients removed from study for unacceptable adverse event(s) will be followed until resolution or stabilization of the adverse event.

5.5 Criteria for Removal from Study

In the absence of treatment delays due to adverse event(s), treatment may continue until one of the following criteria applies:

- Disease progression
- Intercurrent illness that prevents further administration of treatment \geq 14 days or specific changes in the patient's condition that render the patient unacceptable for further treatment in the judgment of the investigator
- Patient non-compliance with protocol requirements (determined via meeting with PI, applicable Sub-I, clinical research coordinator, and patient)
- Unacceptable adverse event(s). Note, a DLT in and of itself may not be an unacceptable adverse event. However, any grade 4 study-drug related AE is unacceptable and will lead to withdraw. The investigator will use his/her opinion, in consultation with the PI, to determine if a study-drug related AE is unacceptable, acceptable, or clinically insignificant (also acceptable).
- Withdrawal of consent (attempts should be made to clarify, with the patient, if withdrawal is specific to study participation, or if it applies to data collection as well). Note: patients lost to follow up (defined as no contact $>$ 60 days after last on-study contact and at least 3 attempts) are considered to have withdrawn study participation consent. Data collection is permissible. Date of last contact will be recorded as the withdrawal date.
- Pregnancy
- Oncoceutics' decision to forgo further drug development of ONC201

The reason for study removal and the date the patient was removed must be documented in the CRF.

Severe adverse events, availability of new adverse toxicology in animals, and financial difficulties due to withdrawal of funds may result in stopping the trial. An investigator, Sponsor, or IRB may take such actions. If the trial is terminated for safety reasons, subjects will be notified immediately and assured that appropriate treatment and follow-up will be available. If an investigator terminates the trial he will inform the Sponsor, subjects, and IRB about the reason for such action. Similarly if the Sponsor terminates the trial, it will inform the investigators, the IRB, and the subjects of the reason for such an action. Similar notifications will be sent by the IRB if it takes such an action.

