6 DOSING DELAYS/DOSE MODIFICATIONS

The descriptions and grading scales found in the revised NCI Common Terminology Criteria for Adverse Events (CTCAE) version 4.0 will be utilized for dose delays and dose modifications.

Below are dose modifications (Table 6.1) for adverse events that are attributable to study drug, including: nausea, vomiting, diarrhea, neutropenia, and thrombocytopenia. If a patient

experiences other adverse events, or several adverse events and there are conflicting recommendations based on Grade, the investigator will use the recommended dose adjustment that reduces the dose. Dose modifications will be made based on an adverse event that occurs during any time during a cycle.

Criteria for disrupting treatment, dose modification, or discontinuation are listed in Table 6.1. Dose modifications are per the clinical judgment of the investigator and agreement of the subject, the treatment will be resumed according to the table below. Dose modification may not be required for adverse events that are clinically manageable.

Table 6.1 Dose adjustment rules for Adverse Events (AEs), including Nausea, Diarrhea, Neutropenia, Thrombocytopenia, and Other AEs. Alopecia does not require dose adjustments.

CTCAE Grade	Management/Next Dose for ONC201
≤ Grade 2	No change in dose
Grade 3 or 4*	Hold until < Grade 2. For first instance, if resolved to < Grade 2 within 21 days resume dosing at 500mg ONC201 and 8mg dexamethasone. For second instance, if resolved to < Grade 2 within 21 days resume dosing at 8mg dexamethasone and 375mg ONC201.**

*Patients requiring a delay of >21 days weeks should go off protocol therapy.

**Patients requiring > two dose reductions should go off protocol therapy.

Participants who experience an adverse event that requires a treatment delay or dose reduction should be monitored with appropriate laboratory testing or other clinical evaluation at least weekly until resolution; if the adverse event does not resolve within 21 days, the interval for testing may be reduced after consultation and written approval by the Overall Principal Investigator (or his designee).

For holds for reasons other than treatment related toxicities, if the participant does not meet criteria to resume treatment within 6 weeks of the event precipitating the hold, the study

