agent(s) may be restarted with approval from the overall Principal Investigator or designee, as long as there has been no significant evidence of disease progression (e.g., by clinical findings, symptoms, tumor markers) during the treatment interruption.

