6.2 Palliative and Supportive Care

All palliative care necessary for optimal care of the patient should be provided. Investigational drug must be held during radiotherapy and for 1 week afterwards. If possible, the investigational drug should be held for 1 week prior to the administration of palliative radiotherapy if possible. It is not known if ONC201 acts as a radiosensitizer or if this would lead to increased toxicity.

However, the potential for ONC201 to act as a radiosensitizer exists. ONC201 should be held for at least one week prior to any elective surgery.

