9.3 Definition of an Adverse Event

An adverse event is any untoward medical occurrence in a clinical investigation patient administered a product or medical device; the event need not necessarily have a causal relationship with the treatment or usage. Examples of adverse events include but are not limited to:

- Abnormal test findings;
- Clinically significant symptoms and signs;
- Changes in physical examination findings;
- Hypersensitivity.

Additionally, they may include the signs or symptoms resulting from:

- Drug overdose;
- Drug withdrawal;
- Drug abuse;
- Drug misuse;
- Drug interactions;
- Drug dependency;
- Exposure in utero;
- Exposure during breast feeding.

Worsening of signs and symptoms of the malignancy under trial should be reported as adverse events in the appropriate section of the CRF. Disease progression assessed by measurement of malignant lesions on radiographs or other methods should not be reported as adverse events

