10 DATA ANALYSIS/STATISTICAL METHODS

10.1 Efficacy Evaluation

All patients who have received a minimum of 2 cycles of study treatment had baseline assessments and at least one on-study tumor assessment following treatment will be considered evaluable for response.

Objective Response Rate (ORR) is defined as the proportion of patients with a Complete (CR) or Partial Response (PR) relative to the total number of evaluable patients. Responses will be defined according to the International Myeloma Working Group response criteria (see Appendix C: Multiple Myeloma Disease Tracking for Myeloma Worksheet).

The best overall response is the best response recorded from the start of treatment until disease progression/recurrence (taking as reference for progressive disease the smallest measurements recorded since the treatment started) or the withdrawal from the study. Stable disease will be considered the best response when observed at least after two months from baseline.

Tumor responses will be analyzed in a descriptive manner. The number and percentage of objective response (CR+PR) will be tabulated by dose level. An ORR may be summarized for the RP2D expansion cohort with the corresponding 95% exact confidence interval.

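### Section 10.1 drops patients who stop early from the ORR denominator, which biases ORR upward against the 10% benchmark; separately, the illness-hold rules need a cross-reference

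*Combined protocol and SAP*

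**What the plan says.** **Denominator.** Section 10.1 defines the evaluable set as "All patients who have received a minimum of 2 cycles of study treatment", with a baseline assessment and at least one tumor assessment on study. ORR is CR plus PR divided by that set. No response rate with all treated patients in the denominator is planned. Section 8.2 tests ORR against a background rate of 10%, with 30% as the rate of interest, 30 patients, one-sided alpha 0.05 and 84% power. Section 3.2 expresses the Phase 2 target as up to 30 evaluable patients. Table 10.1 stops at 26.

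**Holds.** Sections 5.5 and 7.6 list "Intercurrent illness that prevents further administration of treatment" for 14 days or more as a reason to end treatment. Section 5.4 lists the same reason with no duration. Section 6 says: "For holds for reasons other than treatment related toxicities, if the participant does not meet criteria to resume treatment within 6 weeks" of the event, the agents "may be restarted with approval from the overall Principal Investigator or designee", provided there is no significant evidence of progression. Six weeks is therefore the point at which approval is needed, not a cap. What applies before 6 weeks is implied rather than stated.

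**The concern.** The primary endpoint is compared with a fixed external rate, so what the denominator leaves out matters. A patient who progresses, has a serious toxicity, falls ill or withdraws before finishing 2 cycles has usually not responded, and Section 10.1 removes that patient whatever the reason. The remaining set is selected for having done well enough to stay on treatment. If many patients stop early, a regimen no better than background could pass the test more often than the nominal rate suggests, and a reader would have no planned all-treated figure to set beside it.

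The hold wording is a smaller, separate matter. Read literally, an illness hold of 14 days or more that is unrelated to study drug meets both the removal criterion and the restart provision, and the two give opposite instructions.

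**Working it through.** **Inputs.** Benchmark 10%, target 30%, n = 30, one-sided alpha 0.05 (Section 8.2); evaluable definition (Section 10.1). The fraction of treated patients excluded, e, is not in the documents and is assumed.

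**1. Reproduce the plan's figure.** With X binomial, n = 30 and p = 0.10, P(X ≥ 6) = 0.073 and P(X ≥ 7) = 0.026, so success needs 7 responders. Power is P(X ≥ 7) at p = 0.30, which is 0.840. This matches the stated 84%.

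**2. Effect of the denominator on the error rate.** Let the ORR among all treated patients be 10%, and let a fraction e be excluded, all non-responders. The ORR in the evaluable set is then 0.10 / (1 − e). Assume enrollment continues to 30 evaluable patients.

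| Excluded (assumed) | Evaluable ORR | P(X ≥ 7 of 30) |
|---|---|---|
| 0% | 0.100 | 2.6% |
| 10% | 0.10/0.9 = 0.111 | 4.3% |
| 20% | 0.10/0.8 = 0.125 | 7.3% |
| 30% | 0.10/0.7 = 0.143 | 12.6% |

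**3. Effect on the reported ORR with 1 to 3 exclusions (assumed), no replacement.**

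| All treated | Evaluable | Difference (points) |
|---|---|---|
| 6/30 = 20.0% | 6/29 = 20.7% | 0.7 |
| 6/30 = 20.0% | 6/27 = 22.2% | 2.2 |
| 7/30 = 23.3% | 7/27 = 25.9% | 2.6 |
| 5/26 = 19.2% | 5/25 = 20.0% | 0.8 |
| 6/26 = 23.1% | 6/23 = 26.1% | 3.0 |

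**4. Does the test decision change with so few?** Rarely.
- 30 treated, no replacement: one-sided exact p is 0.073 for 6/30, 0.064 for 6/29, 0.055 for 6/28 and 0.047 for 6/27. The decision changes only at exactly 6 responders with three excluded.
- Replacement to 30 evaluable: 7/30 (0.026) becomes 7/33 = 21.2% (0.042) with three counted back, so nothing changes.
- The same test applied at the Table 10.1 maximum of 26, with replacement: 6/26 (0.040) becomes 6/27 (0.047), 6/28 (0.055) or 6/29 (0.064). The decision changes only at exactly 6 responders with two or more counted back.

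All of these figures measure the denominator rule. None measures the choice between hold rules.

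**5. The hold texts side by side.** Sections 5.5 and 7.6 name illness and a 14-day limit. Section 6 names every non-toxicity reason and sets no upper limit. The one precedence statement, at the start of Section 7, ranks the Schedule of Activities over the text of that section, and the Schedule does not address holds. Section 6.2 supplies other holds that the Section 6 provision could serve ("Investigational drug must be held during radiotherapy and for 1 week afterwards", and elective surgery), but nothing confines it to those.

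**The case against.** An evaluable-patient ORR is declared in advance, and the target is counted in evaluable patients, so the plan is consistent with itself. That stands, and it is why the evaluable figure should stay. The exclusion rates are assumed, and with 1 to 3 patients the decision seldom moves; that also stands. The documents give no source for the 10% benchmark. If it came from evaluable patients in similar studies, the inflation in step 2 would be smaller. Nor is the all-treated figure always lower: if one of three patients counted back has a documented early response, 6/27 = 22.2% becomes 7/30 = 23.3%.

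On holds, the specific 14-day criterion can reasonably be read as governing illness, with the general Section 6 provision left for radiotherapy and surgery. Section 5.4 may simply be the shorter statement. Section 5.5 also requires the reason and date of removal in the CRF, so differences in handling can be audited. What remains is a missing cross-reference.

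Two stronger readings are tempting. A reader might infer that the hold ambiguity itself shifts the trial's result. The documents do not support that. They give no rate of such holds, Section 10.1 excludes short-treated patients whatever the cause, and nothing says how a long hold counts towards 2 cycles. A reader might also infer that an unrelated illness ends treatment at 14 days while a drug-related toxicity may be held for 21. That presumes the 14-day rule prevails over Section 6, which is the open question. The reach of Table 6.1 ("Patients requiring a delay of >21 days weeks should go off protocol therapy") is also unclear. Section 6 introduces it "for adverse events that are attributable to study drug", yet its title and the surrounding text extend to other adverse events. Under Section 9.3, "the event need not necessarily have a causal relationship with the treatment or usage", so a severe on-treatment illness might fall under the table.

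**Conclusion.** The denominator point holds as a minor but worthwhile improvement. The evaluable ORR is biased upward as an estimate for all treated patients. The size depends on how many stop early: under 3 points with a few patients in the 30-patient examples, but enough to take the false-positive rate past 5% somewhere between 10% and 20% excluded. This rests on three assumptions: excluded patients are non-responders, the 10% benchmark applies to all treated patients, and enrollment continues to 30 evaluable. The plan's alpha, power and sample size are correctly computed for the evaluable set.

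The hold wording is an editorial note only. Two provisions literally cover the same illness hold and no text ranks them, but a workable reading exists and no result has been shown to depend on it.

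**What to change.** **Section 10.1.** Keep the evaluable ORR. Add the Phase 2 ORR, with its exact 95% confidence interval, among all treated patients. Count anyone who stops before 2 cycles or has no on-study assessment, for any reason, as a non-responder unless a response is documented. This needs no new data, procedures or patients. The cost is a second figure that is usually slightly lower (about 0.7 to 3.0 points with 1 to 3 such patients).

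**Sections 5.4, 5.5, 6 and 7.6.** Add one cross-reference saying whether illness unrelated to study drug follows the 14-day criterion or the Section 6 restart provision, and give Section 5.4 the same limit. The sponsor's clinicians should choose. The sentence should state that drug-related events, including drug-related infection, stay under Table 6.1. It should also say that the opening clause of 5.5 and 7.6 about delays for adverse events does not alter the choice for unrelated illness. The cost is wording only.
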